## 11 SAFETY

### 11.1 Safety Parameters

Clinical and laboratory AEs will be graded using the NCI CTCAE; Version 4.03 (See [Appendix A](#)).

Subjects will be monitored throughout the treatment and follow-up period for occurrence of AEs (acute, delayed, and/or cumulative), as well as for changes in clinical status, vital sign measurements, and laboratory data (including PD). Safety parameters to be measured/assessed include PEs, vital sign measurements, hematology, serum chemistries, urinalysis, and ECG.

### 11.2 Adverse Event Definition

An AE is defined as any untoward medical occurrence in a clinical trial subject associated with the use of a drug, whether considered drug related. An AE can be an unfavorable and unintended sign (e.g., an abnormal laboratory value finding), a symptom, or a disease temporally associated with the use of a drug, without judgment as to causality. An AE can arise from use of the drug (e.g., use in combination with another drug) and from any route of administration, formulation or dose, including an overdose. An AE also includes, but is not limited to, any clinically significant worsening of a pre-existing condition. Examples include:

- Any sign, symptom, physical finding, or laboratory result that has worsened in nature, severity or frequency compared to baseline;
- Reactions from an investigational drug, including those occurring because of an overdose, abuse of the study drug, withdrawal phenomena, sensitivity or toxicity;
- Concurrent illness that was not present or worsens in nature, severity, or frequency compared to baseline;
- Injury or accident; and/or
- Exacerbation of a pre-existing condition.

For data collection, all untoward events that occur after informed consent through 28 days after study drug dosing are to be recorded on eCRFs by the investigational site.

While pregnancy alone is not considered as an AE or SAE, any pregnancy complication(s) should be recorded as an AE(s) or SAE(s) (if applicable). Elective abortions without complications should not be regarded as AEs, unless they were therapeutic abortions (see below). Hospitalization for normal delivery of a healthy newborn should not be considered an SAE. If a female subject becomes pregnant during the conduct of the study, the Investigator must notify the Sponsor according to the procedures provided in [Section 11.3.8](#)).

### 11.3 Evaluating Adverse Events

The Investigator will determine the seriousness, intensity, and causality of an AE associated with the use of the study drug (i.e., events where there is a reasonable possibility that the event may have been caused by the study drug) based on the definitions that follow.

#### 11.3.1 Serious Adverse Events

*(Notify Medpace Safety within 24 hours; document on eCRF)*

The SAE definition and reporting requirements are in accordance with Title 21 Part Code of Federal Regulations (CFR) 312.32 and the Guidance for Industry and Investigators Safety Reporting Requirements for Investigational New Drug (INDs) and Bioavailability /Bioequivalence Studies.

SAE: An AE is considered "serious" if, in the view of either the Investigator or sponsor, it results in any of the following outcomes:

- **Death:** This includes any death that occurs while the subject is "on study" as well as any death that occurs within 28 days after study drug administration.

**Note:** Death is an outcome of an AE, and not an AE. The event(s) that caused death (e.g., illness, accident) is the SAE. Death due to any other cause(s) must also be reported as an outcome of the reportable SAE.

- **Life-threatening adverse drug event:** An AE or suspected adverse reaction is considered "life threatening" if, in the view of either the Investigator or sponsor, its occurrence places the patient or subject at immediate risk of death. It does not include an AE or suspected adverse reaction that, had it occurred in a more severe form, might have caused death.

- **Inpatient hospitalization or prolongation of existing hospitalization:**

In the absence of an AE, the Investigator should not report hospitalization or prolongation of hospitalization. This is the case in the following situations:

- Hospitalization or prolongation of hospitalization is needed for a procedure required by the protocol
- Hospitalization or prolongation of hospitalization is part of routine procedure followed by study center

- Hospitalization for survey visits or annual physicals
- Hospitalization for observation with release within 24 hours

In addition, a hospitalization planned before the start of the study for a pre-existing condition, which has not worsened, does not count as an SAE.

- **Persistent or significant incapacity or substantial disruption of the ability to conduct normal life functions**
- **Congenital anomaly/birth defect**
- **Important medical event:** An event that may not result in death, be life threatening, or require hospitalization may be considered an SAE when, based upon appropriate medical judgment, it may jeopardize the subject and may require medical or surgical intervention to prevent one of the outcomes listed in this definition.

### **11.3.2 Overdose**

An overdose is defined as a significant variation from the recommended/scheduled dosage for a product. The dosing for this study will be conducted in a controlled clinical setting and an overdose is not anticipated. However, in the event of an accident, for this study, an overdose of SYNT001 is considered a dose that is two-fold higher than the intended dose for the subject.

### **11.3.3 Non-Serious Adverse Events**

*(Document on eCRF)*

All other AEs, not fulfilling the previous definitions, are classified as non-serious.

### **11.3.4 Protocol-Related Adverse Events**

AEs that are not test drug related may nevertheless be considered by the Investigator or the Medical Monitor to be related to the conduct of the clinical study. That is, the event may be related to the fact that a subject is participating in the study. For example, a protocol-related AE may be an event that occurs during a screening period or that is related to a procedure required by the protocol.

### **11.3.5 Assessment of Causality**

A medically qualified Investigator must assess the relationship of any AE (including SAEs) to the use of the investigational product, as related or not related, based on clinical judgment and using all available information, and may include consideration of the following factors:

- Possible alternative causes of the AE, including the disease under treatment, pre-existing conditions, concomitant use of other drugs, and presence of environmental or genetic factors.
- The temporal association between drug exposure and onset of the AE.
- Whether the manifestations of the AE are consistent with known actions or toxicity of the investigational product.
- The AE resolved or improved with decreasing the dose or stopping use of the investigational product (dechallenge). Judgment should be used if multiple products are discontinued at the same time.

The causal relationship between the study medication and the AE will be assessed using one of the following categories:

**Not Related:** Factors consistent with an assessment of Not Related include:

- Temporal relationship is lacking (e.g., the event did not occur within a reasonable time frame following administration of the study medication); or
- Other causative factors more likely explain the event (e.g., a pre-existing condition, other concomitant treatments).

**Related:** Factors consistent with an assessment of Related include:

- There is a positive temporal relationship (e.g., the event occurred within a reasonable time frame following administration of study medication); or

The AE is more likely explained by the investigational product than by another cause (i.e., the AE shows a pattern consistent with previous knowledge of the investigational product or the class of the investigational product)

### 11.3.6 Recording Adverse Events

All AEs (including SAEs) are to be accurately recorded on the Adverse Event page of the subject's eCRF. The severity of each AE will be graded using the NCI CTCAE, Version 4.03. The date of onset as well as the end date of the event also should be recorded or the event should be entered as "ongoing". In addition, the method used to treat the AE and the outcome of the AE also will be noted. The Investigator will assess the relationship of the event to study drug.

### 11.3.7 Planned Hospitalization

A hospitalization planned by the subject prior to the first dose of study medication is considered a therapeutic intervention and not the result of a new SAE and should be recorded as medical

history. If the planned hospitalization or procedure is executed as planned, the record in the subject's medical history is considered complete. However, if the event/condition worsens during the trial, it must be reported as an AE.

### **11.3.8 Reporting Pregnancies**

If a female subject or the female partner of a male subject becomes pregnant during the course of the study, the Investigator must report the pregnancy to the Medpace Safety using the **Pregnancy Reporting Form** within **24 hours** of becoming aware of the event. The Investigator must obtain consent to collect pregnancy information (including the status of the newborn, if applicable).

If some of the information required for completion of the Pregnancy Reporting Form is unavailable at the time of the initial report, follow-up reports will be completed and submitted within 24 hours of becoming aware of the new information. Any pregnancy will be followed through delivery for the observation of any SAEs. Any SAE that occurs during pregnancy must be recorded on the SAE report form in the EDC system (e.g., maternal serious complications, therapeutic or spontaneous abortion, ectopic pregnancy, stillbirth, neonatal death, congenital abnormality, birth defect) and reported within 24 hours in accordance with the procedure for reporting SAEs (See Section 11.3.9).

### **11.3.9 Serious Adverse Event Reporting**

#### **11.3.9.1 Governing Regulatory Requirements**

Compliance with this request for prompt reporting is essential in that the sponsor is responsible for informing the US Food and Drug Administration (FDA) and other regulatory authorities as well as all other participating Investigators of the event.

Under FDA ruling (US Code of Federal Regulations, Title 21 CFR Part 312.32) and the ICH Guidelines for Clinical Safety Data Management Definitions and Standards for Expedited Reporting, the sponsor is required to submit written documentation, in the form of a safety report, detailing:

- Any event associated with the use of the drug, that is both serious and unexpected, or
- Any finding from tests in laboratory animals that suggests a significant risk for human subjects, including reports of mutagenicity, teratogenicity, or carcinogenicity.

Written submission must be made by the sponsor to the FDA and the IRBs as soon as possible and in no event later than 15 calendar days after the sponsor's initial notification of the event. The sponsor shall also inform all Investigators.

**11.3.9.2 Time Frame for Reporting**

Any death, SAE, pregnancy, or unexpected (and severe) AE experienced by the subject after informed consent or within 28 days of receiving study drug, regardless of relationship to study drug, or any death that occurs more than 28 days after receiving study drug, and is believed to be study drug related, must be promptly reported (within 24 hours of the Investigator becoming aware of the event) by telephone or electronic transmission to the sponsor (or designee).

Contact information for **SAE** reporting:

Medpace Clinical Safety  
Medpace SAE hotline:  
Telephone: PPD [redacted] dial P or PPD [redacted] dial PPD  
Facsimile: PPD [redacted] D or PPD [redacted]  
e-mail PPD [redacted]

Additionally, the Investigator will be able to contact the **Medical Monitor**:

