	
Exclusion criteria:
 
Subjects meeting any of the following criteria are to be excluded:
 
 
1. Subject unable or unwilling to comply with the protocol;
 
2. Active non-hematologic malignancy or history of non-hematologic malignancy in the 3 years prior to screening (exclusive of non-melanoma skin cancer and cervical cancer in situ);
 
3. Positive for HIV or hepatitis C antibody;
 
4. Positive for hepatitis B surface antigen;
 
5. Active infection or history of recurrent infections;
 
6. IVIG use within 60 days of screening;
 
7. Received any cytotoxic (other than azathioprine) or mAb therapy in the 3 months prior to screening;
 
8. Any exposure to an investigational drug or device within the 30 days prior to screening
 
9. Plasmapheresis or immunoadsorption within 60 days of screening
 

	
10. Cellular therapy at any time prior to screening
 
11. Use of any immunosuppressive drugs apart from corticosteroids, azathioprine, mycophenolate mofetil, or cyclosporine within 3 months of screening
 
12. Serum total IgG < 600 mg/dL;
 
13. Subject has any current medical condition that, in the opinion of the Investigator, may compromise their safety or compliance, preclude successful conduct of the study, or interfere with interpretation of the results (e.g., a significant pre-existing illness or other major comorbidity that the Investigator considers may confound the interpretation of the study results);
 
14. Any vaccination within 2 weeks of screening

Study drug, dosage, and administration	
SYNT001
 
Doses: 10 mg/kg and 30 mg/kg. A third cohort of up to 8 subjects may be treated at another dose, with a maximum dose of 45 mg/kg, but may also be lower than 10 mg/kg or between 10 and 30 mg/kg, inclusive.
 
SYNT001 is provided as a liquid at a nominal concentration of 50 mg/mL. SYNT001 is diluted in Dextrose 5% in Water (D5W) to prepare the solution for infusion.
 
Route of administration: IV in 250 mL over 1 hour

Control, dose, and route of administration	
Not applicable

Duration of subject participation and duration of study	
Up to 70 days (10 weeks): Screening of up to 2 weeks (14 days); dosing period of 4 weeks (28 days); and 4 weeks (28 days) of follow-up

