Safety evaluations will be conducted by a dose escalation committee (DEC). The DEC will consist of the Medical Monitor, an Independent Clinical Expert and a Syntimmune Medical Officer. To assist in the safety assessments, the DEC may request that Investigators, other experts, or members within their organizations review the data and participate in the discussions. Dosing and dose escalation will proceed if the DEC has determined that it would be safe and appropriate to do so. In addition, over the course of the study, the DEC will review any drug-related SAEs to determine if modifications to the study or other measures are necessary to ensure the safety of the subjects.

On days where study drug is administered, vital sign and pulse oximetry measurements will be collected immediately prior to the infusion; 15, 30, and 45 minutes after the start of the infusion; at completion of the infusion; and 30 minutes, 1 hour and 2 hours following completion of the infusion.

On Days 0 and 28, PK blood samples will be collected prior to infusion start and then over the subsequent 48 hours. Subjects will remain at the clinic through the 6-hour PK sample collection and will return to the clinic for the 24- and 48-hour collections. Additional samples will be collected on Days 5 and 33.

On Day 0 photographs will be taken of active lesions. Follow-up photographs will be taken of the same areas on Days 33 and 56. If a subject begins a steroid taper, additional photographs will be taken at the clinic visit during which the decision to begin the taper is made.

Subsequent visits will occur on Days 1, 2, 5, 7, 12, 14, 19, 21, 28, 29, 30, 33, and 42 for safety assessments, study drug dosing, sample collections, and other study procedures.

Subjects also will return to the clinic on Day 56 (28 days after receiving their last dose of study drug) for an End-of-Study/Follow-Up visit.

See [Table 1](#) for a schedule of all study events. To assess safety and tolerability, subjects will undergo physical examinations (PEs; including weight), vital sign measurements, clinical (safety) laboratory tests, AE assessments, concomitant medication assessments, and electrocardiograms (ECG).

**Note:** No vaccinations may be given from within 2 weeks of screening until 2 months following the last dose of study drug.

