### 5.2 Inclusion Criteria

A subject must meet the following criteria to be eligible for the study:

1. Willing and able to read, understand and sign an informed consent form;
2. Male or female  $\geq$  18 years of age;
3. Documented diagnosis of pemphigus vulgaris or foliaceus based on all 3 of the following criteria:
  - a. Documented clinical history consistent with pemphigus vulgaris or foliaceus (clinical presentation defined as mucosal and/ or skin lesions);
  - b. Presence of Anti-Dsg 1 or 3 antibodies above the upper limit of normal;
  - c. History of at least one positive tissue based test (biopsy, DIF)
4. Active disease: Lesions lasting  $>$  2 weeks, and 3 active lesions in skin or mucosa or 2 active lesions with at least one being a skin lesion  $>$  1 cm diameter:
  - a. If treated with rituximab or other anti-CD20 antibodies, last dose  $>$  12 months prior to screening;
  - b. If being treated with other immunosuppressants (i.e., azathioprine, mycophenolate mofetil or cyclosporine), must be on stable dose ( $<$  10% change in dose) for 6 weeks prior to screening;
  - c. If being treated with corticosteroids, must be  $\leq$  1mg/kg/day and stable ( $<$  10% change in dose) for 2 weeks prior to screening;

- d. Allowed topical therapies for pemphigus lesions upon entering the study include petroleum jelly or Aquaphor® for the skin or chlorhexidine for the mouth
5. Body mass index (BMI) 18.5 – 35.0 kg/m^2;
6. Has a negative urine pregnancy test (for women of childbearing potential) documented prior to the first dose of study drug;
7. Females of childbearing potential must agree to be abstinent or else use any two of the following medically acceptable forms of contraception (<1% per year failure rate) from the Screening Period through 60 days after the final study dose: oral contraceptive, condom with or without spermicidal jelly, diaphragm or cervical cap with spermicidal jelly, or intra-uterine device (IUD). A female whose male partner has had a vasectomy must agree to use one additional form of medically acceptable contraception.
8. Females of non-childbearing potential, defined as surgically sterile (status post hysterectomy, bilateral oophorectomy, or bilateral tubal ligation) or post-menopausal for at least 12 months do not require contraception during the study.

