9. Males with female partners of childbearing potential, including males who are surgically sterile (post vasectomy), must agree to be abstinent or else use a medically acceptable form of contraception from the screening period through 60 days after the final study dose.

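### Pregnancy reporting in 11.3.8 and 11.3.9.2 does not clearly cover days 29 to 60 after the last dose, although contraception is required through day 60

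*Protocol*

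**What the plan says.** Three parts of the protocol bear on this.

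- **Contraception period.** Section 5.2 binds women of childbearing potential "from the Screening Period through 60 days after the final study dose". Men with partners of childbearing potential must likewise be abstinent or "use a medically acceptable form of contraception from the screening period through 60 days after the final study dose".
- **Pregnancy section.** Section 11.3.8 is triggered "If a female subject or the female partner of a male subject becomes pregnant during the course of the study". The investigator then has 24 hours from becoming aware, and the pregnancy is followed to delivery.
- **Time-frame section.** Section 11.3.9.2 covers "Any death, SAE, pregnancy, or unexpected (and severe) AE experienced by the subject after informed consent or within 28 days of receiving study drug". The one event it names beyond that limit is "any death that occurs more than 28 days after receiving study drug, and is believed to be study drug related".

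Section 4.3 places the end of the study at "Day 56 (28 days after receiving their last dose of study drug) for an End-of-Study/Follow-Up visit". The Synopsis agrees, with 28 days of follow-up after the dosing period. The last scheduled pregnancy test is on Day 56 (Section 6.7.1 and Table 1). Section 11.2 states that a pregnancy is not in itself an AE or SAE.

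**The concern.** The protocol asks both sexes to avoid conception until day 60 after the last dose, yet both reporting rules appear to stop at about day 28. A site that learned of a conception on, say, day 45 would find no clear duty to report it.

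Follow-up to delivery under Section 11.3.8 starts with a report. Without one, the course and outcome of that pregnancy may never reach the sponsor, although it began in a period when the protocol itself asks subjects to avoid pregnancy. The point concerns the capture of safety data. No endpoint, analysis, sample size or dose-escalation decision depends on it.

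**Working it through.** **Inputs**

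- Contraception after the last dose: 60 days (Section 5.2, both sexes).
- Reporting after the last dose: 28 days (Section 11.3.9.2), or to the end of the study (Section 11.3.8).
- Schedule: screening up to 14 days, dosing 28 days, follow-up 28 days (Synopsis).
- Visit window for Day 56: plus or minus 5 days (Section 7.16 and Table 1).

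**The protocol's own figures**

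- 14 + 28 + 28 = 70 days, as stated in the Synopsis.
- Day 56 − Day 28 = 28 days, as stated in Section 4.3.

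The two reporting rules therefore end at the same nominal point.

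**The gap**

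- Uncovered days = 60 − 28 = 32, that is, days 29 to 60.
- Share of the post-dose contraception period: 32/60 = 53%.
- Share from first dose: 32/(28 + 60) = 32/88 = 36%.
- Share from the start of a full 14-day screening: 32/(14 + 28 + 60) = 32/102 = 31%.

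If the study ends for a subject at the actual final visit, with the last dose on Day 28:

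- Visit on Day 51: 60 − 23 = 37 days (62% of 60).
- Visit on Day 61: 60 − 33 = 27 days (45% of 60).

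**Does another rule close the gap?**

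- Section 11.3.9.3 keeps SAEs assessed as related recordable after 28 days, and Section 6.10 does the same for known related untoward events. Because of Section 11.2, an uncomplicated pregnancy triggers neither.
- Section 7.17 adds visits at about 2 and 3 months after the last dose, but only for tetanus or VZV antibody retesting. Table 1 schedules no pregnancy test at them.

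**Subject or partner?** Section 11.3.8 includes the female partner of a male subject. Section 11.3.9.2 refers only to what the subject experiences. The two sections therefore differ on whose pregnancy is covered as well as on how the period is described.

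**The case against.** The strongest case for leaving the text alone has five parts.

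1. **The time-frame wording is open-ended.** Its two limbs are joined by an *or*, and the one that starts at informed consent has no end date. Read literally, a later pregnancy is covered. This stands as a criticism of the wording. It does not settle the matter, because the separate clause for later drug-related deaths would then be largely redundant, and the AE and SAE periods in Sections 11.2 and 11.3.9.3 are 28 days.
2. **The periods need not match.** A precautionary contraception period may be longer than a reporting period. Section 9.6.2 expects IgG to return to normal within 4 weeks, from Phase 1a data after a single dose and from primate data after repeated doses. This stands: no passage says that the two periods must be equal, and the difference is not in itself a contradiction.
3. **The most exposed pregnancies are covered.** Section 11.3.8 turns on when conception occurs, with the clock running from awareness. A conception during dosing or the next 28 days is reportable even if found later. This stands.
4. **Serious outcomes have a partial backstop.** Congenital anomaly is an SAE criterion, and Section 11.3.8 lists stillbirth, spontaneous abortion and birth defect as SAE examples. After 28 days, however, the rule needs a judgement that the event is related, and it does not start follow-up of the pregnancy itself.
5. **The yield is small.** With no routine contact after Day 56, a wording change captures only what a site happens to learn.

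A reader might infer that more than half of a fetal-risk window goes unrecorded. The documents do not support that. The 53% applies only to the nominal post-dose segment, and the Day 56 visit window moves it between 45% and 62%. The share of the whole contraception period is 31%. The protocol nowhere describes days 29 to 60 as a period of fetal risk, and its discussion of immune effects in Section 9.6.2 does not mention the fetus.

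**Conclusion.** The point holds as a gap in clarity and coverage. Sections 11.3.8 and 11.3.9.2 do not clearly require a report of a pregnancy that begins on days 29 to 60 after the last dose, while Section 5.2 requires contraception throughout those days. The uncovered span is 32 of 60 post-dose days.

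This rests on two readings: that 28 days is the intended limit in Section 11.3.9.2, and that the course of the study in Section 11.3.8 ends at Day 56 for subjects without extended visits. If either phrase was meant more broadly, the text still needs correcting, because a site could reasonably read it the narrower way.

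The importance is low. At most 27 subjects of both sexes may be enrolled (Section 5.1), so few pregnancies are expected. The case for acting is that the correction is cheap and would bring such a pregnancy, if the site learns of it, into the follow-up to delivery that Section 11.3.8 already provides.

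**What to change.** Amend Sections 11.3.8 and 11.3.9.2 so that both give one pregnancy-reporting period, matched to the contraception period already in Section 5.2. Any pregnancy in a subject, or in the female partner of a male subject, that begins up to 60 days after the last dose and becomes known to the site would be reported within 24 hours of awareness and followed to delivery. In the same edit, give pregnancy its own sentence in Section 11.3.9.2, with an explicit end date and an explicit mention of partners.

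The change is one of wording only. It adds no visit or test and leaves dosing and the contraception requirement as they are. The cost is at most a rare additional report and its follow-up.
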